#### CONFIDENTIAL AND PROPRIETARY

## **Clinical Protocol - Device**

A Prospective Multi-Centre Study in Patients Undergoing Total Knee Replacement Version: 2.0, 02Jun2021 with JOURNEY II CR Total Knee System Page: 18 of 57

- JOURNEY II CR Articular Inserts which are available in sizes 1-2, 3-4, 5-6, and 7-8 in right and left designs, and offered in 9-18 mm thicknesses and manufactured from cross-linked polyethylene (XLPE) material.
- JOURNEY II Deep Dished Inserts, cruciate substituting (deep dished) articular inserts, which are available in sizes 1-2, 3-4, 5-6, and 7-8 in right and left designs with 9-21mm thicknesses and manufactured from cross-linked polyethylene (XLPE) material.

Study Number: Journey II CR.2020.11

JOURNEY II Knee components are supplied sterile for single use only. Components do not incorporate medicinal substances, tissues, or blood products, nor is it present in the manufacturing process.

JOURNEY II CR total knee system was first approved by FDA in 2012.

The JOURNEY II CR Total Knee System consists of femoral component made from oxidized zirconium (OXINIUM) will be used for this study.

Figure 6-1. JOURNEY II CR Total Knee System (OXINIUM)

## **6.2 Product Use**

Please refer to IFU of the JOURNEY II CR Total Knee System for full instructions.

## 6.3 Packaging and Labelling

Packaging and labeling will be prepared to meet regulatory requirements. Package integrity and labelling should be verified prior to use of the product and confirmed in the eCRF.

## 6.3.1 Labelling

JOURNEY II CR Total Knee System (Oxinium) is commercial product for sites in India, China mainland, China (Hong Kong), Singapore, Thailand and Japan. Packaging and labelling will be prepared per the standard commercial packaging and local regulatory requirements.

#### CONFIDENTIAL AND PROPRIETARY

## **Clinical Protocol - Device**

A Prospective Multi-Centre Study in Patients Undergoing Total Knee Replacement Version: 2.0, 02Jun2021 with JOURNEY II CR Total Knee System Page: 19 of 57

## **6.4 Product Accountability Procedures**

This study is a post-market study but OXINIUM Femoral component is supplied by the Sponsor in China sites and accountability procedure should be followed in China sites.

China investigational sites will maintain an inventory of the IP/Ancillary Products and Study Supplies.

The Sponsor or its designee will provide a log(s) to facilitate IP/Ancillary Products and Study Supplies inventory control. All IP/Ancillary Products and Study Supplies accountability logs must be retained in the Investigator Site File (ISF). These records must be available for inspection by the Sponsor, its designees, or by regulatory agencies at any time.

Study Number: Journey II CR.2020.11

The Study Monitor will ensure that the procedures and records are in place for the appropriate reconciliation of all IP/Ancillary Products and Study Supplies. As part of monitoring, the Study Monitor will check that site personnel are following the proper procedures for accountability and completing all necessary documentation.

Only the product components provide by sponsor need to follow the accountability procedure, for the components purchased by investigational site, no product accountability procedure will be applied.

## 6.5 Surgical Technique

All study related procedures with the JOURNEY II CR Total Knee System must be performed according to the surgical technique and IFU of the specific Smith+Nephew Implant System.

Surgeons selected to participate in this study will be familiar with the JOURNEY II CR Total Knee System and have written evidence of training and expertise in the study procedure. Pre-study cases shall be performed until the surgeon feels comfortable with the system in order to prevent any learning curve during the study. The number of pre-study cases depends on the level of the individual experience of the surgeon.

#### **6.6 Medical Procedure**

All surgical related procedures with the JOURNEY II CR Total Knee System must be performed according to the surgical technique and IFU of the specific Smith+Nephew Implant System.

#### 7 SUBJECT ENROLLMENT AND WITHDRAWAL

## 7.1 Subject Population

A total of up to 480 knees' information will be collected in up to 15 sites in India, China mainland, Hong Kong, Singapore, Thailand and Japan There will be up to 240 knees for resurfaced patella group and up to 240 knees for un-resurfaced patella group.

| Group | # of sites | Resurfaced Patella | Un-resurfaced Patella |
|-------|------------|--------------------|-----------------------|
|-------|------------|--------------------|-----------------------|

#### CONFIDENTIAL AND PROPRIETARY

## **Clinical Protocol - Device**

A Prospective Multi-Centre Study in Patients Undergoing Total Knee Replacement Version: 2.0, 02Jun2021 with JOURNEY II CR Total Knee System

Study Number: Journey II CR.2020.11

Page: 20 of 57

| Up to 480 knees (JOURNEY II CR | Up to 15 | Up to 240 knees | Up to 240 knees |
|--------------------------------|----------|-----------------|-----------------|
| TKA)                           |          |                 |                 |

#### 7.2 Inclusion Criteria

Subjects will be considered qualified for enrollment if they meet the following criteria:

- Subjects with degenerative Osteoarthritis. 1.
- 2. Subject is planning to have TKA using JOURNEY II CR.
- 3. Subject is able and willing to provide voluntary consent to study participation.
- 4. Subject is 18-80 years old (inclusive).\*
- \* For Japan, the minimum inclusion age is 20 years old.

#### 7.3 Exclusion Criteria

Any one (1) of the following criteria will disqualify a potential subject from participation in the study:

- 1. Subjects with rheumatoid arthritis/inflammatory arthritis, posttraumatic arthritis
- 2. Previous surgeries including HTO, UKA or TKA on the subject knee
- 3. Subject is pregnant or breast feeding or those at a child-bearing age planning to become pregnant during the follow up.
- 4. Subject does not meet the indication or is contraindicated for JOURNEY II CR's IFU.

## 7.4 Screening

Participating study sites are required to document all screened subjects considered for inclusion in this study. If a subject is excluded from the study, the reasons for exclusion will be documented in the subject's source documents and noted on the Screening and Enrollment Log.

## 7.5 Informed Consent

Before conducting any study procedures or examinations, the purpose and nature of the study should be explained to the subject in their native language.

The subject, or their legally authorized representative, will then **read**, **sign**, and **personally date** the IRB/IEC-approved informed consent document(s) (see below for difficulties with reading and writing). Additionally, the individual who obtains

#### CONFIDENTIAL AND PROPRIETARY

## **Clinical Protocol - Device**

A Prospective Multi-Centre Study in Patients Undergoing Total Knee Replacement Version: 2.0, 02Jun2021 with JOURNEY II CR Total Knee System

Study Number: Journey II CR.2020.11

Page: 21 of 57

consent from the subject will sign and date the informed consent document. A copy of the signed informed consent document will be provided to the subject, a copy will be placed in the subject's medical record, with the original filed in the ISF.

If the subject is unable to read, the informed consent document and associated study information may be read aloud to the subject in the presence of an impartial witness. If possible, the subject shall sign and personally date the Informed Consent Form (ICF). Where this is not possible, due to difficulties in writing, the subject shall provide verbal consent to participate in the study. The witness shall then personally sign and date the informed consent form, attesting that the information was accurately explained and that the informed consent was freely given.

#### 7.6 Enrolment

Subjects for whom the consent process has been completed and have been treated with the study product are considered enrolled.

Subjects that provided informed consent but do not receive the study treatment for any reason will be considered as screen failure.

## 7.7 Lost to Follow-up

A subject will be considered lost to follow-up if he/she does not appear for the scheduled study visit for 2 consecutive visits, and study personnel are unable to contact the subject.

Some actively enrolled subjects will not return for follow-up exams on time. Study personnel must make a reasonable effort to contact the subject and document the following contact attempts before declaring a subject to be lost to follow-up: the subject has been contacted according to the site's policies, but no fewer than two documented phone contacts and one certified letter without response. Copies of all attempts to reach the subjects by mail or email and/or the attempts to contact the subject via other means should be documented, and that documentation should be kept with the subject's source documents.

#### 7.8 Withdrawal

#### 7.8.1 Withdrawal from Treatment

Subjects may be withdrawn early from study treatment for the following reasons:

- At the discretion of the Investigator due to:
  - o A change in treatment is clinically warranted
  - o An adverse event
  - o Any other significant reason identified by the Investigator

#### CONFIDENTIAL AND PROPRIETARY

## **Clinical Protocol - Device**

A Prospective Multi-Centre Study in Patients Undergoing Total Knee Replacement Version: 2.0, 02Jun2021 with JOURNEY II CR Total Knee System Page: 22 of 57

## 7.8.2 Withdrawal from Study

The Investigator may withdraw subjects from the study for many reasons, including but not limited to the following:

Study Number: Journey II CR.2020.11

- Subject noncompliance (e.g., did not follow instructions)
- Subject lost to follow-up
- The Investigator or the Sponsor stops the study for any reason and decides to withdraw subject(s) from the study
- Concurrent illness
- Adverse Events/Adverse Device Effects
- Any other significant reason identified by the Investigator

For each case, information will be obtained in the source document and the Case Report Form (CRF), detailing circumstances leading to the withdrawal.

Subjects who drop out or are withdrawn will not be re-entered into the study at a later date.

If at any point during the study, the prosthesis needs to be revised for any reason the following will apply: Subjects shall continue to have follow-up visits in order to monitor the subject's health status. Potential data following the revision surgery will not be included as study data but presented separately as safety data.

For minor revisions, where not the whole knee implant system is replaced (e.g. replacement of inserts) the subject shall continue with the study specific schedule and data will be presented.

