7.2 Analysis Populations

The following are the analysis populations included in the protocol:

- Safety Population (SAF): This is defined as all subjects who were enrolled and treated with the study devices.
- Intent-to-Treat Population (ITT): The ITT population is defined as subjects from SAF, who have at least one post-operative assessment on any of the effectiveness endpoints.
- Per-Protocol Population (PP): The PP population is a subset of subjects in the ITT population, who do not have major protocol deviations and who satisfied all enrolment eligibility criteria. All major protocol deviations will be formally classified on a case-by-case basis prior to the final study database lock.

However, due to premature termination of the study, all analyses will be performed with SAF population only.

CONFIDENTIAL AND PROPRIETARY

Statistical Analysis Plan

A Prospective Multi-Centre Study in Patients Undergoing Total Knee Replacement with JOURNEY II CR Total Knee System Number: Journey II

CR.2020.11 ST: ST1197

Version: V1.0, 20-MAY-

2024

Page: 10 of 20

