7.3 Handling of Missing, Incomplete and Repeat Data

All data will be analysed as observed unless stated otherwise in analysis section.

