7.6 Disposition Data

A table will be provided summarising number of subjects.

Subject (and knee) disposition will be summarized after completion of the study using frequency (n) and percentage (%) of subjects (or knee) who completed and who did not complete the study. For those who did not complete the study, the primary reason for discontinuation will additionally be summarized.

CONFIDENTIAL AND PROPRIETARY

Statistical Analysis Plan

A Prospective Multi-Centre Study in Patients Undergoing Total Knee Replacement with JOURNEY II CR Total Knee System Number: Journey II

CR.2020.11 ST: ST1197

Version: V1.0, 20-MAY-

2024

Page: 16 of 20

The number of knees that enter the study, and the number of knees with follow up information will be provided by visit:

- Theoretically due: number enrolled and implanted with study device
- Deaths: cumulative number of subjects that died prior to the study visit
- Revisions / failures: cumulative number of subjects that revised/failed prior to the study visit
- Cumulative terminations: terminated from study other than from revision or death
- Expected = theoretical due cumulative (deaths + revisions + termination)
- Actual = actual number of subjects at follow up visit
- Follow up = actual / expected x 100.

The number of subjects that have discontinued from the study and reasons for withdrawal will be summarised.

Study duration and the duration between surgery and each visit will be summarised.

Screening and enrolment summary: For each centre/site, dates that the first subject was screened/enrolled and the last subject completed will be provided, duration (site, 1st enrolled – final subject exit), together with number of subjects enrolled and number of subjects completed 10 year visit.

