7.10 Analysis of Primary Endpoint(s)

The protocol states:

CONFIDENTIAL AND PROPRIETARY

Statistical Analysis Plan

A Prospective Multi-Centre Study in Patients Undergoing Total Knee Replacement with JOURNEY II CR Total Knee System Number: Journey II

CR.2020.11 ST: ST1197

Version: V1.0, 20-MAY-

2024

Page: 17 of 20

The primary endpoint of this study is the OKS at 2 years. If we assume the mean of OKS at 2 years for the subjects with implant JOURNEY II TKA with and without Patella Resurfaced as $\mu 1$ and $\mu 2$. The hypothesis test will be as following:

H0: μ 1 = μ 2 vs

H1: $\mu 1 \neq \mu 2$

The mean difference (μ 1- μ 2) and 95% CI will be estimated. If zero is included in 95% CI of mean difference, then null hypothesis will be accepted, which means patella resurfacing has no impact on the outcomes of JOURNEY II TKA. Otherwise if zero is not included in 95% CI of mean difference, then alternative hypothesis (H1) will be accepted, which means patella resurfacing has significant impact on the outcomes of JOURNEY II TKA. If the lower limit of 95% CI is greater than 0, which means that the subject implant with Patella Resurfaced has higher OKS at 2 years. If the upper limit of 95% CI is less than 0, which means that the subject implant with Patella Resurfaced has lower OKS at 2 years.

In addition, the mean and 95% CI of OKS at 2 years for subjects implant with and without Patella Resurfaced will be estimated separately.

At time of writing the SAP, this study has been early terminated, the study no longer has sufficient power for this hypothesis test to be relevant and it will therefore not be performed. Summary statistics, 95% CI for $\mu 1$ and $\mu 2$ would be presented.

The primary endpoint will be summarized using the SAF population only due to premature termination.

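### The SAP follow-up rate subtracts revised subjects from Expected but not from Actual, although the protocol keeps them attending, so the rate can be overstated

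*Protocol*

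**What the plan says.** **Protocol 7.8.2** sets two rules for a revised prosthesis.

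- After a revision, visits go on: "Subjects shall continue to have follow-up visits in order to monitor the subject's health status". The later data are set apart: "Potential data following the revision surgery will not be included as study data but presented separately as safety data".
- After a minor revision, where only part of the implant system is replaced, "the subject shall continue with the study specific schedule and data will be presented".

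**SAP 7.6** builds the follow-up rate for each visit. Its revision row reads "Revisions / failures: cumulative number of subjects that revised/failed prior to the study visit" and does not separate full from minor revisions. Expected is the number theoretically due less cumulative deaths, revisions and terminations. (The minus sign appears to have been lost in the text available to me, and I read it as a subtraction.) Actual is the number of subjects seen at the visit, with no mention of revision. The rate is Actual divided by Expected, times 100.

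**On which values enter the summaries**, SAP 7.3 says "All data will be analysed as observed unless stated otherwise in analysis section". SAP 7.2 says "However, due to premature termination of the study, all analyses will be performed with SAF population only", and defines that population thus: "This is defined as all subjects who were enrolled and treated with the study devices". SAP 7.10 repeats the choice for the primary endpoint: "The primary endpoint will be summarized using the SAF population only due to premature termination". SAP 7.10, 7.11 and 7.13 do not restate the protocol's rule on data after a full revision and plan no separate display of such data. Revisions get a listing and, if feasible, Kaplan-Meier estimates. SAP 7.15 lists only the dropping of statistical tests as a change from the protocol.

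**The concern.** A follow-up rate is meaningful only if everyone in the numerator could also be in the denominator. Under SAP 7.6 a revised subject leaves the denominator at revision. Under Protocol 7.8.2 that subject may still attend and so be counted in the numerator. The rate then rises with each revised subject who attends, and follow-up looks more complete than it is.

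The mismatch is firmest for minor revisions. The protocol keeps these subjects fully on study, and the SAP's revision row does not exempt them.

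The second matter is smaller. A programmer working from the SAP alone finds the safety population, as-observed data and no exception for fully revised knees. That programmer could leave OKS, KSS and FJS values in the summaries after the original prosthesis has been replaced. With hypothesis testing dropped, the cohort means with 95% intervals are what remains of the primary analysis, so it should be plain which values feed them.

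**Working it through.** The documents give no follow-up figure, revision count or post-revision OKS, so there is no plan figure to reproduce. Everything below is illustrative. The 240 knees per cohort and the ±1.2 OKS precision come from SAP 6.1. Revision counts, attendance and OKS deficits are assumed. I take one knee per subject and no deaths.

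**Follow-up rate.** Let D be the number due, T the terminations, R the revised, a the unrevised subjects seen and v the revised subjects seen.

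- As written: (a + v) / (D − T − R)
- Matched, revised out of both terms: a / (D − T − R)
- Matched, revised in both terms: (a + v) / (D − T)

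The excess of the first over the second is v / (D − T − R).

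*Example:* D = 240, T = 0, R = 5, 200 seen including all 5 revised.

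- As written: 200/235 = 85.1%
- Out of both: 195/235 = 83.0%
- In both: 200/240 = 83.3%
- Excess over the out-of-both rate: 5/235 = 2.1 percentage points

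If fully revised knees leave both terms and minor revisions stay in both, the result lies between 83.0% (all five full) and 83.3% (all five minor).

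*When the rate passes 100%:* this happens when more revised subjects attend than unrevised, non-terminated subjects miss the visit. With T = 0 and full attendance:

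| Revised | As written | Either matched count |
|---|---|---|
| 2 | 240/238 = 100.8% | 100.0% |
| 5 | 240/235 = 102.1% | 100.0% |
| 12 | 240/228 = 105.3% | 100.0% |

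Formal terminations do not prevent it, because they also leave Expected. With T = 48 (20% of 240) and R = 5, and everyone else attending, the rate is 192/187 = 102.7%.

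**OKS mean.** If a share r of the knees in the mean are fully revised and score d points lower, keeping them lowers the cohort mean by r × d.

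| Assumed r | Assumed d | Shift in mean | Share of 1.2 |
|---|---|---|---|
| 1% | 5 | 0.05 | 4% |
| 1% | 10 | 0.10 | 8% |
| 2% | 10 | 0.20 | 17% |
| 3% | 15 | 0.45 | 38% |
| 5% | 15 | 0.75 | 63% |

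The last two rows pair high values of both assumptions. The 1.2 is the precision planned for a full cohort. The study ended early, so it serves only as a yardstick.

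**The case against.** **Numerator.** The SAP does not say that revised subjects are counted in Actual. It describes terminations as those for reasons other than revision or death, which may mean that its authors saw revision as an exit from follow-up. On that view revised subjects leave both terms and the ratio is coherent. This stands in part: the mismatch follows from reading SAP 7.6 literally beside Protocol 7.8.2, and is not stated. But the exit view does not fit a protocol that continues visits after revision, and fits least for minor revisions, which stay on schedule with their data presented.

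**Post-revision scores.** A reader might infer that the SAP contradicts the protocol and that the two texts give different primary means. The documents do not support that. SAP 7.3 stands under a heading on missing, incomplete and repeat data and reads naturally as a no-imputation rule. The SAP says it serves Protocol Version 2.0, and SAP 7.15 does not revoke the exclusion. The protocol rule therefore still holds, and the SAP has left it out.

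**Hidden failures.** A reader might also infer that excluding post-revision scores conceals failures. It does not: the exclusion was set in the protocol, revisions are listed, and SAP 7.6 tabulates them cumulatively by visit.

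**Size.** In the first example (240 due, none terminated, 5 revised and all 5 attending), at least 231 of the other 235 (98.3%) must attend before the rate passes 100%, since 236/235 = 100.4%. That is demanding, though formal terminations are already out of Expected. No decision in the SAP depends on this rate.

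**Conclusion.** The follow-up formula in SAP 7.6 needs correcting. As written, it subtracts revised or failed subjects from Expected and does nothing to remove them from Actual, while Protocol 7.8.2 keeps them attending. It can therefore overstate follow-up, by about 2 percentage points in the assumed example (85.1% against 83.0% to 83.3%), and it can pass 100% when nearly all expected subjects attend. If no revised subject attends, the numerator holds no unmatched subjects.

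The handling of PROM values after a full revision is an omission in the SAP and not a conflict with the protocol. It matters only if a fully revised knee has a later score on file. Its effect on the 2-year OKS mean is unknown and probably small: 0.05 to 0.20 points for 1% to 2% revised with a deficit of 5 to 10 points, all assumed.

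This is a minor point, worth making because the repair is almost free.

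**What to change.** 1. **SAP 7.6.** Use the same knees in Expected and Actual at each visit. Remove knees fully revised before the visit from both terms and keep minor-revision knees in both. Define full and minor revision as in Protocol 7.8.2. Count knees throughout, because the section introduces a table of knees and then defines several rows by subjects.
2. **SAP 7.10 and 7.11.** State that PROM values after a full revision are left out of the summaries and shown separately as safety data, and that data after a minor revision are retained.
3. **SAP 7.13.** Name the listing or table that will hold the post-revision data.
4. **Optional.** Add a row giving the 2-year OKS mean with post-revision values included. The documents do not call for it.

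The cost is a few sentences of SAP text and a small programming change. No new data are needed.
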